Boosting vaccination uptake using wastewater surveillance: a comparison-control trial

Utilizing wastewater surveillance data in a communications campaign as a driver behind COVID-19 vaccine uptake in New York State

INVESTIGATORS

Principal Investigator

[name] MPH
Syracuse University
[name]
[name]
[contact]
Email: [contact]

Co- investigators

[name]
Center for Environmental Health, New
York State Department of Health
CDC Foundation
Email: [contact]

[name]
Department of Public Health,
Syracuse University
Email: [contact]

[name]
Department of Public Health,
Syracuse University
Email: [contact]

[name]
Center for Environmental Health, New
York State Department of Health
CDC Foundation
Email: [contact]

[name]
Syracuse University
Department of Public Health
Email: [contact]

[name]
Center for Environmental Health, New
York State Department of Health
CDC Foundation
Email: [contact]

[name]
Syracuse University
Department of Public Health
Email: [contact]

INVESTIGATORS	2
PROJECT SUMMARY	4
RATIONALE AND BACKGROUND	5
Objectives	6
TARGET COUNTIES	7
INTERVENTION	7
EVALUATION	7
Study Design	7
Selection of control and treatment counties	7
Outcomes	8
Data to be collected	9
Statistical analyses	9
TIMEFRAME	10
HUMAN SUBJECTS RESEARCH	10
Risks to subjects	10
Adequacy of protection against risks	10
Potential benefits of the proposed research to the subjects and others	10
Data and safety monitoring plan	10
Inclusion of women and minorities	11
Inclusion of children	11
Trial Registration	11
Protocol Accessibility	11
Funding Stream	11
Conflict of Interest Statement	12
Ethical approval	12
APPENDICES	12
Appendix 1 – Letter of Cooperation from New York State Department of Health	12
Appendix 2 – Letter of Cooperation from Local Health Departments	12
REFERENCES	12

PROJECT SUMMARY

Goal	To determine the effect of a communications campaign sharing wastewater surveillance data to influence vaccine uptake in a metropolitan and non-metropolitan environment.
Intervention site	Onondaga and Cayuga counties in New York State
Populations	Individuals of all ages within the selected counties, located in metropolitan and non-metropolitan environments.
Evaluation study design	Comparison-control trial
Primary outcome measures	Proportion of vaccine-eligible individuals in the county that received the COVID-19 vaccine stratified by type of vaccine dosage and age group

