Data collection and sampling method	Vaccination data will be aggregated to the county by the State Department of Health and shared with the research team. Wastewater data will be pulled from the wastewater surveillance network.
Statistical and analytic plan	A difference in differences analysis will be used to estimate the effect of the intervention on both the outcomes between intervention and comparison groups following the intervention, while adjusting for potential confounding factors.

RATIONALE AND BACKGROUND

Vaccinations are among the most successful and critical public health interventions. The expanded program for immunizations is responsible for preventing an estimated 4-5 million deaths globally, and capable of preventing an additional 1.5 million deaths with universal global coverage.^{1,2} Despite the enormous protection that vaccines provide to public health, delays and refusals of vaccines (vaccine hesitancy) are on the rise.^{3,4} Vaccine hesitancy leads to lower community-level vaccination rates which threaten resurgences of vaccine-preventable diseases such as polio or measles and increase the severity of seasonal infectious diseases such as influenza.^{5,6} The drivers of vaccine hesitancy are complex, and can vary heavily between different demographic groups. Reasons for vaccine hesitancy tend to fit into three categories: 1) a lack of confidence in effectiveness, safety, system, or policy makers; 2) a perceived lower risk of acquiring a vaccine preventable disease; and 3) a lack of availability, accessibility, and convenience in obtaining a vaccine.^{7,8}

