Wastewater surveillance of SARS-CoV-2 has been shown to be a leading indicator of pending surges. Our work in New York State shows that the variability in wastewater data precedes surges in COVID-19 cases by about four weeks (Moran et al. in preparation). This study will examine whether a communications campaign based upon SARS-CoV-2 wastewater surveillance data with a 4-week lead time to surges can increase COVID-19 vaccine uptake.

Objectives

The goal of this trial is to test the effect of a communications campaign based upon wastewater surveillance data on COVID-19 vaccine uptake.

This protocol presents a plan for conducting a strategic communications campaign to identify the impact of sharing public health messaging based upon wastewater surveillance data on COVID-19 vaccination uptake. The specific objectives of this project are to:

1. Assess the impact of a communications campaign on the outcomes of COVID-19 vaccine uptake, including initial dose, complete series, booster dose, and bivalent booster dose by age group, following implementation of the communications campaign in selected metropolitan and non-metropolitan counties.
2. Strengthen the capacity of the New York State Department of Health and local health departments in determining how to apply their resources to disseminate wastewater surveillance data effectively with the general population.

INTERVENTION COUNTIES

The comparison control trial to assess a communications campaign using wastewater surveillance data will be conducted in Onondaga County (metropolitan) and neighboring Cayuga County (non-metropolitan) in New York State. Monroe and Seneca Counties will serve as a comparison to Onondaga and Cayuga Counties, respectively. These counties were selected based on similarities across population density, demographics (age, sex, race, ethnicity), wastewater surveillance population coverage, and vaccination rates.

INTERVENTION

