		Metropolitan Counties		Non-Metropolitan Counties	
		Monroe	Onondaga	Seneca	Cayuga
COVID-19 vaccine coverage	Primary Series	74.0	74.0	53.9	60.8
	Up to Date	17.3	15.9	11.4	12.0
Social vulnerability index	Socioeconomic Status	0.4426	0.4918	0.4918	0.6066
	Household Characteristic	0.8525	0.7377	0.5738	0.3443
	Racial & Ethnic Minority Status	0.8361	0.7377	0.4754	0.4262
	Housing Type & Transportation	0.4754	0.7541	0.4098	0.7213
Pharmacies	per 10,000 People	1.87	2.21	1.46	2.08
Population	Number	743084	461591	34016	76958
	Density per sq mile	1125.1	590.2	105.81	110.47
Income	Median Household Income (\$)	65,957	65,541	54,865	63,511
Vaccination data as of 11/18/22 from: https://coronavirus.health.ny.gov/vaccination-progress-date					
People with primary series represents the total number of individuals who have completed the recommended initial series of a given COVID-19 vaccine product (e.g., 2 doses of the 2-dose Pfizer or Moderna vaccine; 1 dose of the single dose Johnson & Johnson vaccine).					
People up to date represents the total number of individuals who have completed all COVID-19 vaccinations, including the bivalent booster, as appropriate per age and clinical recommendations (CDC At-A-Glance COVID-19 Vaccination Schedules).					
Social Vulnerability Index from: https://www.atsdr.cdc.gov/placeandhealth/svi/interactive_map.html					
Theme rankings: For each of the four themes, we summed the percentiles for the variables comprising each theme. We ordered the summed percentiles for each theme to determine theme-specific percentile rankings.					
Population 2020 Estimates					

Outcomes

The communications campaign will be evaluated using the change in vaccination status of residents of the treatment and control counties. Change in vaccination status will be

broken down by type of vaccine dose (e.g., initial series v. booster dose) and age because vaccine eligibility varies by age group (Table 2).¹⁹

Table 2: Proposed age and vaccine dose breakdown for vaccination outcomes.		
Age group	Primary Series	Up to Date with bivalent booster
18+	85.2	12.3
12-17	73.1	4.2
5-11	39.6	1.9
Under 5	6.2	--

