Notes: People with primary series represents the total number of individuals who have completed the recommended series of a given COVID-19 vaccine product (e.g., 2 doses of the 2-dose Pfizer or Moderna vaccine; 1 dose of the single dose Johnson & Johnson vaccine). People up to date represents the total number of individuals who have followed and completed the all COVID-19 vaccinations, including the bivalent booster, as appropriate per age and clinical recommendations ([CDC At-A-Glance COVID-19 Vaccination Schedules](#)). Vaccination progress tracking in New York was updated 11/30/22 to reflect the most current ACIP recommendations.

Data from <https://coronavirus.health.ny.gov/demographic-vaccination-data>

The change in vaccination coverage among residents of the counties in the study will be measured as the percent of the population that received a vaccine dose. Outcomes will also be compared between demographic groups including race and ethnicity because of differences in vaccination rates that have been already observed.²⁰

Data to be collected

All data used in this study is routinely gathered and disseminated by the New York State Department of Health. No individual human data will be collected as part of the study.

Statistical analyses

We will use a difference-in-differences (DiD) method to evaluate the effectiveness of the communications campaign using the following equation:

$$DiD = E(Y_1^T - Y_0^T | T_1 = 1) - E(Y_1^C - Y_0^C | T_1 = 0)$$

The DiD is calculated from the differences between the treatment group ($T_1 = 1$) and the control group ($T_1 = 0$) from their initial condition at $t = 0$ or time zero. The change in each group is compared to determine if the intervention resulted in different outcome in the treatment group. In our study, the outcome is the percent of the county populations that received COVID-19 vaccines during the study period and whether the treatment counties had greater vaccination rates by the end of the study than the control counties. We will determine the statistical significance for DiD using a regression framework where the mean vaccination rate (Y) is predicted by whether the county received the treatment (the communications campaign) or not. The mean will be determined for the total vaccination rate as well as each of the age categories identified in Table 2.

TIMEFRAME

Table 3: Time frame for proposed activities

Project Years:	2022				2023			
	Q1	Q2	Q3	Q4	Q1	Q2	Q3	Q4

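### No test is named to decide the trial: the primary outcome is split by dose and age, with no alpha and no multiplicity rule

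*Combined protocol and SAP*

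**What the plan says.** The Project Summary gives one primary outcome measure, worded as a set of strata: "Proportion of vaccine-eligible individuals in the county that received the COVID-19 vaccine stratified by type of vaccine dosage and age group". Its analytic plan row says that DiD will "estimate the effect of the intervention on both the outcomes between intervention and comparison groups", without saying which two outcomes are meant.

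Objective 1 lists uptake "including initial dose, complete series, booster dose, and bivalent booster dose by age group", which is four dose types. In the Outcomes section, the measure of change is "broken down by type of vaccine dose (e.g., initial series v. booster dose) and age because vaccine eligibility varies by age group". The accompanying Table 2, titled "Proposed age and vaccine dose breakdown for vaccination outcomes", has two dose columns and four age rows. The same section adds: "Outcomes will also be compared between demographic groups including race and ethnicity".

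The Statistical analyses section plans formal inference: "We will determine the statistical significance for DiD using a regression framework". It ends with the list of means: "The mean will be determined for the total vaccination rate as well as each of the age categories identified in Table 2".

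No section states an alpha or a sidedness, calls one test primary, sets a testing order or adjusts for multiplicity. Trial Registration and Protocol Accessibility place registration and submission of the protocol to a journal before the campaign is delivered. The second is meant, among other things, to prevent selective reporting of outcomes.

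**The concern.** A trial that tests several means and names none as decisive has no fixed meaning for a positive result. Two analysts could both follow this plan and report different headline findings, for example the total rate or the 12-17 age group. If only a stratum crossed the chosen threshold, presenting it as the primary result would not depart from the protocol, because the primary outcome is itself defined by strata.

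Advance publication does not close this gap. It lets a reader compare the report with the plan, but a plan that ranks no test cannot show which result was meant to decide.

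The total rate is the natural candidate, but as written it does not identify one test. It is not tied to a dose type. Its denominator is vaccine-eligible individuals in the Project Summary and the county population in the Statistical analyses section.

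**Working it through.** The plan states no alpha, power or family-wise error, so there is no figure of its own to reproduce.

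**Inputs from the documents**
- Means listed in Statistical analyses: the total plus the four Table 2 age groups (18+, 12-17, 5-11, under 5), so 1 + 4 = 5.
- Filled cells in Table 2: four for primary series and three for up to date (the under-5 cell is a dash), so 4 + 3 = 7. The plan does not list these as tests.

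**Assumptions, none stated in the documents**
- Two-sided 5% per test, with each test holding its level.
- Normal test statistics, equally correlated between strata (correlation r).
- The total is a weighted sum of the four age strata. Two weightings were tried: equal weights, and 80% on adults.

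**Five means.** The four age strata alone, if independent, give 1 - 0.95^4 = 0.185. The total adds little because it is built from the same strata. Let Z be the four stratum statistics with correlation matrix R, and w the weights. The statistic for the total is then w'Z / sqrt(w'Rw). Simulating all five and counting any value beyond 1.96 in absolute size gives:

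| r between strata | Chance of at least one false positive |
|---|---|
| 0 | 19% (80% adult weight) to 20% (equal weights) |
| 0.5 | 16% |
| 0.8 | 11% |
| 0.95 | 8% |

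**Seven cells, if they were tested.** Independent: 1 - 0.95^7 = 0.302. Equally correlated normal statistics, by numerical integration: 0.230 at r = 0.5, 0.149 at 0.8 and 0.092 at 0.95.

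**Two checks on the seven-cell figures**
- Counting only results that favour the campaign (2.5% each) gives 0.162 when independent and 0.046 at r = 0.95, against 0.025 for a single test.
- With a two-versus-two county t test (2 degrees of freedom), correlation helps less: about 0.136 at r = 0.95, against 0.092 for normal tests.

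As r approaches 1, every two-sided figure falls to 5%. The low ends quoted here are the values at r = 0.95 and are not absolute minima. Race and ethnicity comparisons are not counted, because the plan does not give their number.

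**The case against.** The best defence is that the plan implies a hierarchy. It names the total first and puts the question at county level. It explains the age split by eligibility. It says that children are not a major focus and that no significant race or ethnicity difference in effect is expected. This makes a child or ethnic-group headline less in keeping with the plan, and that much stands. It does not rank a test: the only outcome labelled primary is the stratified one, and the age-specific means directly follow the sentence on significance testing, with nothing marking them as descriptive.

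A second objection is that the strata share four counties and one campaign, so high correlation is more credible than independence. That is reasonable and favours the lower figures, although the documents give no correlation.

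Third, with two counties per arm and no stated variance method, a single test may not hold 5%. This also stands. It is the prior problem: if it is not solved, the percentages do not describe this study, and naming one primary test does not make that test valid.

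Some stronger readings are not supported:
- A reader might apply 1 - 0.95^5 = 23% to the five means. That needs five independent tests, and the total is not independent of its own strata.
- A reader might take 30% as the plan's error rate, or multiply four dose types by four ages to get 16 tests. Neither seven nor 16 is given as a list of tests.
- A reader might infer an intention to select a favourable stratum. Nothing in the documents suggests it; the plan only fails to rule it out.

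**Conclusion.** The point holds as a gap in specification that affects how the result can be read. The textual part needs no assumption: the primary outcome is a family, significance testing is planned, and neither a deciding test, an alpha nor a multiplicity rule is given. The size is illustrative only: about 8% to 20% for the five listed means over correlations from 0.95 to 0, and about 9% to 30% if all seven filled cells of Table 2 were tested. Both ranges depend on the assumed 5% level, on each test holding it, and on the correlation.

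The mismatches in dose lists and denominators concern the definition of the outcome. They do not enter these percentages. They matter here because they leave the total without a unique meaning. The change should be made, but it ranks below the question of valid inference from two counties per arm.

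**What to change.** Before registration and launch, name one primary test at a stated alpha and sidedness: the DiD for the total rate, for one dose type and one denominator. The investigators choose the dose type and the denominator, and use them consistently in the Project Summary, Objective 1, Outcomes with Table 2, and Statistical analyses. Replace the reference to two unnamed outcomes in the Project Summary with the outcomes meant.

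Make the age-specific, other-dose and race or ethnicity results secondary, reported as estimates with intervals. If the investigators want stratum-level claims, test those only after the primary test, in a fixed order or with a Holm adjustment.

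The cost is wording in the protocol and the registration entry. No new data are needed, and the plan already places registration and protocol submission before the campaign. The downside is that single age or dose strata can no longer support unadjusted stand-alone claims. The change does not settle whether the primary test itself holds its level with two counties per arm; that needs its own answer.
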